### 6.5 Follow-up

Collection from daily recordings will be undertaken either prospectively or retrospectively to assess adverse event and efficacy of therapy from day 1 (1st day of treatment) to day 10 and then weekly while admitted to the treatment centre and then 30 days post last dose. For patients for whom therapy is discontinued prior to day 10, assessments will follow the same schedule to allow comparison of disease course.

The following will be recorded, as permitted, starting immediately prior to the onset of administration of IFN  $\beta$ -1a, then on a daily basis whilst the patient is in the treatment centre:

- Temperature; fever will be defined as a temperature  $\geq 38$  °C.
- Concurrent illness symptoms: chills, myalgia, cough, sore throat, nausea, vomiting, diarrhea, hemaorrhage.
- Adverse events will be recorded per protocol. Medication history at baseline and daily will be recorded.
  - Blood samples:
    - 20 cc of Blood for virologic measurement (if feasible).
    - A convalescent serum (10 cc tiger top tube) will be obtained at 1 month (when possible).
  - Survival

Of note, it is expected that there will be missing data points for study participants depending on the clinical care data available in the medical chart and residual blood samples available for testing.

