### 8.3 Adverse Event Definitions and Reporting

Adverse Event (AE): is any untoward medical occurrence in a patient or clinical investigation participant administered a product. It does not necessarily have to have a causal relationship with this treatment. An AE can therefore be any unfavorable and unintended sign (including an abnormal laboratory finding, for example), symptom or disease temporally associated with the use of a medicinal product, whether or not considered related to the medicinal product.

All adverse events will be recorded and transcribed into the CRF. Solicited AEs and non-solicited AEs will be collected daily for the first four days and then every 2-3 days during therapy, or whenever reported by patients. SAEs will be collected while on study medication and for 30 days after administration of the last dose.

**Serious Adverse Event (SAE):** is any adverse event that:

- is fatal
- is life-threatening
- results in persistent or significant disability/incapacity
- requires initial hospitalization or prolongation of existing hospitalization
- causes congenital anomalies or birth defects

The term "life-threatening" refers to an event in which the patient was at risk of death at the time of the event. It does not refer to an event, which hypothetically might have caused death, if it were more severe. All deaths occurring while on protocol therapy or within 30 days of the last dose, should be reported (see below).

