### 9.2 Secondary

**Safety:** Occurrence and severity of adverse event; time to onset, duration (number of days), severity, and seriousness of solicited and non-solicited injection site reactions and systemic adverse events occurring up to 7 days after the last injection. Occurrence, nature, time to onset relative to the first IFN  $\beta$ -1a dose, duration, severity, relationship to injection of SAEs throughout the trial.

- The frequency of clinically important (moderate or severe) adverse events will be compared between the groups
- The frequency of serious adverse events will be compared between the groups.

Parameters to look for adverse events will be solicited such as local injection site erythema and swelling, fever, heart rate, blood pressure, and rash.

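### Sections 8.3 and 6.5 set different adverse-event collection frequencies after day 4, so brief events outside the daily symptom list may be under-recorded in days 4-7 and 8-10

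*Protocol*

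**What the plan says.** Four parts of the protocol bear on this point.

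- **Section 8.3:** solicited and non-solicited adverse events are to be "collected daily for the first four days and then every 2-3 days during therapy", and it adds "or whenever reported by patients".
- **Section 6.5:** the opening sentence reads "Collection from daily recordings will be undertaken either prospectively or retrospectively to assess adverse event and efficacy of therapy from day 1" and runs to day 10, then weekly while the patient is admitted. It is followed by a list of items to be recorded, as circumstances permit, before the first dose and "then on a daily basis whilst the patient is in the treatment centre". The list names temperature, chills, myalgia, cough, sore throat, nausea, vomiting, diarrhea and hemorrhage. Its adverse-event item says only "Adverse events will be recorded per protocol".
- **Section 9.2:** the secondary endpoint includes "time to onset, duration (number of days), severity, and seriousness of solicited and non-solicited injection site reactions and systemic adverse events". The solicited parameters are injection-site erythema and swelling, fever, heart rate, blood pressure and rash.
- **Section 10.2:** days 0-3, 4-7 and 8-10 are analysed separately, and each participant contributes the worst report within each period.

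The protocol does not say whether a contact after day 4 covers the whole interval since the previous contact or only the day of the contact.

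**The concern.** A site cannot tell from the document whether adverse events after day 4 are to be collected daily or every two to three days. The choice affects the secondary endpoint. Onset and duration are wanted in days, and the analysis is split into periods whose first boundary lies almost exactly where the 8.3 schedule thins out. If 8.3 is followed, ascertainment in the first period differs from that in the other two. A short event is then more likely to be missed late in treatment than early, whatever the drug does.

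Safety is the secondary objective (Section 4) and one of the factors that decide whether the pilot is extended (Section 16). The safety profile by period should therefore not depend on which section a site happened to follow.

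**Working it through.** The protocol gives no figure on this point, so there is nothing to reproduce. The check counts contacts and then asks how often a short event would meet one.

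**Inputs.** The contact rule is from 8.3. The periods are from 10.2. Day 1 is the first day of treatment (6.5). Because 10.2 starts its first period at day 0, a count from day 0 is shown as well.

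**Step 1: contact days under 8.3, to day 10.**

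| Count from | Gap after the daily phase | Contact days | Days 0-3 | Days 4-7 | Days 8-10 |
|---|---|---|---|---|---|
| Day 1 | 2 days | 1, 2, 3, 4, 6, 8, 10 | 3 of 3 | 2 of 4 | 2 of 3 |
| Day 1 | 3 days | 1, 2, 3, 4, 7, 10 | 3 of 3 | 2 of 4 | 1 of 3 |
| Day 0 | 2 days | 0, 1, 2, 3, 5, 7, 9 | 4 of 4 | 2 of 4 | 1 of 3 |
| Day 0 | 3 days | 0, 1, 2, 3, 6, 9 | 4 of 4 | 1 of 4 | 1 of 3 |

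Under daily recording, as in 6.5, every day of every period has a contact.

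**Step 2: chance that an event meets a contact.** Assume the worst case: a contact records that day's status only, there is no recall, and patients report nothing in between. Onset is taken as equally likely on each day of the period. The chance is the number of onset days for which the event is still present at a contact, divided by the days in the period.

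| Event length | Count from | Days 0-3 | Days 4-7 | Days 8-10 |
|---|---|---|---|---|
| 1 day | Day 1 | 100% | 2/4 = 50% | 1/3 to 2/3 = 33-67% |
| 1 day | Day 0 | 100% | 1/4 to 2/4 = 25-50% | 1/3 = 33% |
| 2 days | Day 1 | 100% | 75-100% | 67-100% |
| 2 days | Day 0 | 100% | 50-100% | 67% |
| 3 days | Day 1 | 100% | 100% | 100% |
| 3 days | Day 0 | 100% | 100% | 67% |

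The one shortfall for three-day events is an onset on day 10 when the last contact was on day 9.

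**Step 3: chance of at least one positive contact.** If an event is present on any given day with probability p, independently between days, the chance over k contacts is 1 - (1 - p)^k. The value of p is an assumption, since the protocol gives none. The table counts from day 1.

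| p | Days 0-3 (k = 3) | Days 4-7, 8.3 (k = 2) | Days 4-7, daily (k = 4) | Days 8-10, 8.3 (k = 1 or 2) | Days 8-10, daily (k = 3) |
|---|---|---|---|---|---|
| 0.05 | 14% | 10% | 19% | 5-10% | 14% |
| 0.10 | 27% | 19% | 34% | 10-19% | 27% |
| 0.20 | 49% | 36% | 59% | 20-36% | 49% |

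For example, at p = 0.10: 1 - 0.9^3 = 0.271, 1 - 0.9^2 = 0.19, 1 - 0.9^4 = 0.344.

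**Step 4: error in dates.** With contacts g days apart, g - 1 days between them go unobserved. A start or stop known only from contacts is therefore uncertain by up to 1 day (g = 2) or 2 days (g = 3) at each end. For example, with g = 3, an event seen only on day 7 may have begun on day 5, 6 or 7 and ended on day 7, 8 or 9. Its duration could be anything from 1 to 5 days.

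**Step 5: which events are exposed.** Of the parameters solicited in 9.2, only fever is also on the daily list of 6.5, through temperature. Injection-site erythema and swelling, heart rate, blood pressure and rash are not on that list.

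**The case against.** The case on the other side is substantial and limits the point in five ways.

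- **Other routes of capture.** 8.3 also takes events when patients report them and requires all adverse events to be entered in the case report form. This stands, so the figures in Step 2 are a worst case. It helps less for heart rate and blood pressure, which patients do not notice reliably, and for participants who are very ill, whom Section 5.1 expects to be common.
- **Daily symptom data exist.** Fever, chills, myalgia and the other listed symptoms are recorded daily under 6.5. The most common drug reactions named in 2.3.1 (chills, fever, myalgia and asthenia) are, apart from asthenia, on that list. This stands and confines the problem to events off the list.
- **The clash may be softer than it looks.** The adverse-event item in 6.5 may simply refer back to 8.3, or 6.5 may mean charting while 8.3 means transfer to the form. This stands only in part, because the opening sentence of 6.5 names adverse events and daily recordings without any such qualifier.
- **No test across periods is planned.** 10.2 calls for separate analyses by period and comparisons between groups. This stands, so the harm lies in how the periods are described and read side by side.
- **Resources are limited.** Sections 6.2 and 11 say so, and 6.5 expects missing data. This is a reason to offer a fallback, not to leave two rules in place.

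A reader might infer that duration in days cannot be measured at all, or that later periods are bound to show fewer events. The documents support neither. Durations can still be obtained from onset and stop dates, patient reports or the chart. Events of three days or more are almost always met. Nothing says that contacts record one day's status only. Nor is a steady decline implied: counted from day 1 with two-day gaps, the two later periods have two contacts each.

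**Conclusion.** Sections 8.3 and 6.5 disagree on how often adverse events are collected after day 4, and they need to be reconciled. If 8.3 is followed, scheduled contacts counted from day 1 fall from 3 of 3 days in the first period to 2 of 4 and then 1-2 of 3. Short-lived events outside the daily symptom list may then be under-recorded in the two later periods, and their onset and duration are less precise.

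The size depends on an unstated matter, namely what a contact covers. At worst, between a third and two thirds of one-day events would be missed in days 8-10 and half in days 4-7, counting from day 1. Counting from day 0, the losses are two thirds and 50-75%. If each contact asks about the whole interval with dates, or the daily chart is used, the loss shrinks to recall or charting error. This is a moderate point of consistency and measurement, and it is worth correcting before data collection.

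**What to change.** Change the sentence in 8.3 so that adverse events are recorded daily through day 10 while the patient is in the treatment centre, as 6.5 already states, with onset and stop dates for each event. In 6.5, replace the adverse-event item with an explicit reference to that rule.

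If daily collection is not feasible, keep the two-to-three-day contacts but require each one to cover the whole interval since the last, with onset and stop dates, and amend 6.5 to match. In that case, note beside the results by period that the number of scheduled contacts differs between periods.

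The cost is one sentence in each section and a short daily form entry, on days when an injection is already given, generally by the patient's nurse (6.3). The fallback adds no visits but relies on recall, which is weak for vital signs and for very ill patients.

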### **2.3.2 Procedures to Minimize Risks**

Alcohol swabbing of the skin prior to venipuncture and IFN  $\beta$ -1a injection, and use of sterile disposable needles and syringes will minimize the risk of infection. Applying pressure over needle puncture sites to minimize bruising should also be carried out. Exclusion of patients who have previously experienced a severe allergic reaction to IFN  $\beta$  preparations, and since participants will probably remain in the treatment centres for the duration of treatment, trained personnel will be available in case for allergic reactions post-injection.

For the first ten (10) ebola-infected subjects to receive IFN  $\beta$ -1a, a staggered administration schedule will be used to minimize the effect of any unforeseen serious adverse events in this patient population. The second patient will not be administered IFN  $\beta$ -1a until the first subject has received five (5) doses. Likewise, the third subject will not be administered IFN  $\beta$ -1a until the second subject has received 5 doses. If, in the opinion of the treating physician and the Special Access Program in Conakry, Guinea, no unforeseen serious adverse events are observed five (5) days after the tenth subject has received IFN  $\beta$ -1a, more than one of the remaining

subjects enrolled/to be enrolled in the study may receive their first dose of IFN  $\beta$ -1a on the same day.

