### **Rare Adverse Events (<1% frequency)**

Severe psychiatric adverse events may develop in persons receiving therapy with IFN  $\beta$ -1a and includes suicidal ideation and suicide. The risk of this happening is small and less than 1%.

IFN- $\alpha/\beta$  has on occasion exacerbated pre-existing cardiovascular disease, and has caused angina (chest pain), rhythm disturbances or heart attacks (myocardial infarction) in these persons. In those with known pre-existing heart disease, physicians will monitor for cardiac symptoms closely and discontinue IFN  $\beta$ -1a if cardiovascular symptoms appear to be worsened by the drug.

IFN  $\beta$ -1a has rarely been associated with ophthalmic problems, including retinal hemorrhages, optic neuritis and papilledema in persons on long-term treatment. Participants will be asked to report to their physician any disturbance in vision while they are on treatment.

IFN  $\beta$ -1a may exacerbate liver disease and will be discontinued with grade 4 hepatotoxicity.

Very rarely IFN  $\beta$ -1a has been associated with pulmonary syndromes including pneumonia and worsening of asthma. If a participant develops worsening pulmonary symptomatology, which is felt to be due to IFN  $\beta$ -1a then the drug will be dose-reduced or stopped.

IFN  $\beta$ -1a may aggravate autoimmune diseases (for example, systemic lupus or rheumatoid arthritis), and those with pre-existing autoimmune disease will be closely monitored.

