### **Management of Adverse Events**

Management of adverse events is generally achieved by dose reduction of IFN  $\beta$ -1a, however, in the case of life-threatening adverse events, development of cardiac dysfunction, or precipitous decline in pulmonary function over a 24 hour period, which is not explained by disease progression and which may be associated IFN  $\beta$ -1a, therapy will be discontinued.

Flu-like symptoms can be treated with acetaminophen 500-1000 mg or ibuprofen 200-400 mg 30 minutes before IFN  $\beta$ -1a injection.

The following guidelines will be used to determine when dose modification of the investigational product for an adverse event should be implemented.

- Grade I (mild) adverse events: No dosage adjustment
- Grade 2 (moderate) adverse events: No dosage adjustment
- Grade 3 (severe) adverse events: Patients who develop grade 3 adverse events (except flu like symptoms, unless they are incapacitating) should have IFN  $\beta$ -1a reduced to 3 MIU (15 mcg). Alternatively, IFN  $\beta$ -1a may be discontinued.

- Grade 4 (Life threatening) adverse events (SAE): IFN  $\beta$ -1a will be discontinued.

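### The SAE definition in Section 8.3 has no medically important event criterion, so some severe but not immediately life-threatening harms may miss 24-hour reporting and the SAE count

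*Protocol*

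**What the plan says.** Protocol Section 8.3 lists five SAE criteria. An event is serious if it is fatal, is life-threatening, "results in persistent or significant disability/incapacity", "requires initial hospitalization or prolongation of existing hospitalization", or "causes congenital anomalies or birth defects". The list ends there, and no further criterion appears elsewhere in the protocol. The second criterion is then narrowed: life-threatening "refers to an event in which the patient was at risk of death at the time of the event".

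Under SAE Reporting in the same section, SAEs go to the study coordinator and the manufacturer within 24 hours, and the report to the coordinator is meant to allow notice to the Ministry of Health within 7 calendar days. No other adverse event carries that duty. On the collection window, Section 8.3 says "SAEs will be collected while on study medication and for 30 days after administration of the last dose". Section 9.2 compares SAE frequency between the groups and, as a separate item, the frequency of moderate or severe adverse events.

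Section 8.2 warns of specific harms. Under Rare Adverse Events it states "Severe psychiatric adverse events may develop in persons receiving therapy with IFN" β-1a, naming suicidal ideation and suicide, and it goes on to cardiac, eye, liver, lung and autoimmune effects. Section 2.3.1 lists hepatic injury among the potential risks. In the dose-modification guide of Section 8.2, the SAE label appears at one grade only: "Grade 4 (Life threatening) adverse events (SAE").

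**The concern.** An SAE definition has to pick out the events that someone outside the ward must hear about quickly. This one depends on death, immediate risk of death, incapacity and hospitalization. In a population that is already admitted, hospitalization does less of that work than usual. A grave event that neither threatens life at that moment nor disables the patient may then fall outside the list, although the protocol itself flags that kind of event.

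Section 2.3.3 states that IFN β-1a has not been given to patients with Ebola virus infection before. Prompt central notice of a serious non-fatal effect is therefore worth having, even if such effects are rare. The between-group SAE count would also omit those events.

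**Working it through.** The protocol states no figure on this point, so there is nothing to reproduce. The check sets the texts side by side, then gives a rough scale.

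**1. How the hospitalization criterion works here.** Admission to the treatment centre is an inclusion criterion (Section 5.3), so a first hospitalization cannot occur during the stay. Section 6.3 expects most stays to last at least 7 days because of the illness, and treatment itself runs 7 to 10 days. Prolongation by a drug effect is listed and can be claimed, but it is hard to separate from the Ebola stay. After discharge, a re-admission within 30 days of the last dose would count. The criterion is weak in this setting but not empty.

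**2. Named harms against the five criteria.**

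- *Already SAEs:* suicide; a fatal or life-threatening myocardial infarction; grade 4 hepatotoxicity, through the Section 8.2 label; an eye event causing persistent or significant incapacity.
- *May meet none of the five:* suicidal ideation; angina or arrhythmia without risk of death; grade 3 hepatic injury; transient eye events; worsening asthma; autoimmune flare.
- *Set beside life-threatening events by the protocol:* Section 8.2, Management of Adverse Events, lists new cardiac dysfunction and an abrupt 24-hour fall in lung function as alternatives to life-threatening events when it says therapy will be discontinued, provided that disease progression does not explain them and IFN β-1a may be involved. Neither is an SAE unless it also meets a Section 8.3 criterion. An event that triggers that rule may thus carry no 24-hour duty.

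**3. What such an event loses and keeps.** It loses the 24-hour report (Section 8.3) and its place in the SAE comparison (Section 9.2). It keeps its entry in the case report form and its causality assessment (Section 8.3). If moderate or severe, it also keeps its place in the separate adverse event comparison (Sections 8.4 and 9.2).

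**4. Scale.** The Rare Adverse Events heading gives a frequency below 1%, and the text repeats that bound for severe psychiatric events. I assume p = 0.1%, 0.5% or 1% per event type. The sample size is 30 to 50 (Section 10.1), with a possible extension to 100 (Section 16). The chance of at least one event is 1 − (1 − p)^n:

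| n | p = 0.1% | p = 0.5% | p = 1% |
|---|---|---|---|
| 30 | 3.0% | 14.0% | 26.0% |
| 50 | 4.9% | 22.2% | 39.5% |
| 100 | 9.5% | 39.4% | 63.4% |

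For example, with n = 30 and p = 1%, 1 − 0.99^30 = 0.260. The expected count n × p runs from 30 × 0.001 = 0.03 to 50 × 0.01 = 0.5 per event type in the planned 30 to 50 patients.

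**The case against.** The best defence is that the definition and the other safety measures catch more than they may seem to. Much of it stands.

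- A reader might infer that the severe harms named in the protocol are simply not SAEs. The text does not support that. Their fatal, life-threatening, grade 4, incapacitating and stay-prolonging forms qualify. The disability criterion reads persistent or significant, so a transient but significant incapacity counts.
- A reader might take the Section 8.2 label to mean that only grade 4 events are SAEs. That passage is a dose-modification guide: it calls grade 4 an SAE and does not exclude lower grades. The risk is one of misreading.
- A reader might infer that the staggered-start check in Section 2.3.2 is defeated as well. That check asks that "no unforeseen serious adverse events are observed five (5) days after the tenth subject". Harms already listed are foreseen, so their absence from the SAE definition has little bearing on it.
- A reader might infer that these events go uncollected after treatment. Section 6.5 schedules adverse event assessment to 30 days after the last dose. Section 8.3, however, describes routine adverse event collection only during therapy, and the endpoint in Section 9.2 stops 7 days after the last injection.
- The moderate or severe comparison keeps these events in the safety results, and Section 10.2 analyses the two grades grouped. This restores the counting but not the 24-hour notice.
- Of these named harms, Section 8.2 calls only the psychiatric events severe. It ties eye effects to long-term treatment and describes lung effects as very rare. Section 5.4 excludes several at-risk groups, although it lets the treating physician review the exclusions.
- Section 13 adopts ICH GCP, but its text is not in the protocol, so no conflict with it is claimed.

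**Conclusion.** The point holds in a limited form. The five-criterion list has no place for a medically important event, and its hospitalization criterion discriminates weakly among inpatients. Followed as written, some severe but not immediately life-threatening events may miss expedited reporting and the SAE count. They are not lost from the safety data.

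Few cases are expected: a 3% to 26% chance of at least one per event type with 30 patients, and 5% to 39% with 50. These figures rest on the assumed 0.1% to 1% rates. A rate of several percent would give much larger chances, but the protocol's own bound for the rare events does not support one. The figures are also rough in two directions. Several event types together would raise the chance, while some events under that heading are SAEs already. The protocol gives no rate for cardiac dysfunction or pulmonary decline as used in its management rules.

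The case for change therefore rests on one missed report mattering in a first-use pilot, and on the low cost of the remedy.

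**What to change.** - **Section 8.3:** add a sixth criterion, for example: *is medically important in the investigator's judgement because it may jeopardise the patient or need intervention to prevent one of the outcomes above*. Update the SAE form to match.
- **Section 8.2:** state that the SAE label on grade 4 does not limit SAEs to grade 4.
- **What to avoid:** do not make every harm named in Sections 2.3.1 and 8.2 an automatic SAE at grade 3 or above. Those sections also name fever, chills, myalgia, headache and nausea. Severe Ebola-like symptoms would then become SAEs by rule and swamp the signal.
- **Section 9.2:** because the comparison group comes from retrospective records (Sections 5 and 6.1), a criterion based on judgement cannot easily be applied to both groups alike. Report the between-group SAE comparison on the existing five criteria as well.

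The cost is a sentence or two, a revised form, a few more 24-hour reports and one additional tabulation. These are changes to reporting definitions only; no dose or stopping rule is affected.
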